## 10.3 Patient and Demographic Data

#### 10.3.1 Baseline Characteristics and Demographics

Summary descriptive statistics for baseline and demographic characteristics will be provided for all enrolled subjects, according to the NIH guidelines.

Statistical presentation for baseline and demographic characteristics may be further summarized and will be further defined in the statistical analysis plan (SAP).

#### **10.3.2 Medical History**

Medical history will be collected, including the existence of current signs and symptoms and clinical significance for each body system. Numbers and rates of patients with history of each condition will be reported.

#### **10.3.3 Use of Medications**

All medications used will be coded using the World Health Organization (WHO) drug dictionary. The number and percentage of subjects receiving concomitant medications or therapies will be presented.

#### 10.3.4 Study Completion

The percent of subjects who complete the study, losses to follow-up, times to lost to follow-up, and reasons for discontinuation (e.g., adverse events) will be presented. Statistical presentation of study completion may be further summarized by reasons for withdrawal and study site and will be further defined in the statistical analysis plan (SAP).

## 10.4 Sample Size and Power Calculations

The selected sample size is 18 subjects in each of the 2 arms. Historical data on 10 subjects from The University of Alberta suggest a standard deviation in the control group of approximately 0.9 nmol/L. Power calculations assumed that a two-sided 5% level t-test with equal variances would be used for the analysis. Based on a standard deviation of 0.9 nmol/L, this study will have 90% power to detect a difference of 1.0 nmol/L between the mean for the LMW-DS treatment group and the mean for the control group. The study will be able to detect a difference of 0.9 nmol/L with 80% power.

## 10.5 Interim Analyses to Ensure Patient Safety

The NIDDK DSMB will be convened to review safety data periodically. When an official interim analysis is requested the DCC will prepare interim analyses that will include distributions of primary and secondary endpoints, biomarkers and adverse events by treatment group. Safety reports will

summarize all reported serious adverse events and adverse events. Adverse events will be summarized for each body system and for all body systems combined. Additional analyses may be requested by the DSMB.

# 10.6 Statistical Guidelines for Terminating the Study

We have prepared a monitoring plan based on using the Lan and Demets alpha spending method with an O'Brien-Fleming spending function . This strategy accounts for the multiple analyses associated with the interim monitoring and allows the DSMB to request analyses at times that are not fixed at the beginning of the study. The method is very conservative early and therefore has very little effect on the overall power of the study. The details of the monitoring plan are included in the SAP.

Table 6 displays an example using this strategy with planned interim analyses when 12 subjects (6 in each group) have finished the 75 day follow-up period, a second interim analysis when 24 subjects (12 in each group) have finished, and a final analysis when all 36 subjects have completed the 75 day follow-up. These calculations were based on a 5% two-sided t-test to compare two independent means and no stopping for futility. The program PASS  was used to calculate the values in the table.

This strategy recommends stopping after 12 subjects have completed 75 days if the standard z-test for a difference in the two means exceeds 3.71 in absolute value. This is equivalent to requiring that the p-value for the test is less than or equal to 0.0002. The plan would recommend stopping after 24 subjects, if the absolute value of the test statistic exceeds 2.51. This requires an observed p-value less than or equal to 0.0120. If the plan recommends stopping after either interim analyses and the difference is in favor of the LMWDS group then one would conclude that LMWDS is superior to the control. If the difference is in favor of the comparison group then one would conclude that LMWDS is inferior to the control. The stopping boundaries for this example are displayed in Figure 5.

At the final analysis one would conclude that LMWDS is superior to the control if the difference is in favor of LMWDS and the p-value is less than or equal to 0.0463. If the difference is in favor of the comparison group and the p-value is less than or equal to 0.0463 then one would conclude that the LWMDS is inferior to control. If the p-value is greater than 0.0463 then one would conclude that there is not enough evidence to conclude that the two interventions are different.

Interim	Number of		ary Values . Z Test	Associated p-value		
Analysis	subjects completing 75 day follow-up	Lower Boundary	Upper Boundary			
1	12	-3.71	3.71	0.0002		
2	24	-2.51	2.51	0.0120		
3	36	-1.99	1.99	0.0463		

Table 7. Stopping Boundary Values

[figure not shown]

Figure 5. Stopping Boundary

Should the effect be found to cross the monitoring boundary before the end of the study, the DSMB will advise NIH on whether enrollment should be terminated early. Subjects already enrolled in the study will continue with their assigned treatment unless the DSMB recommends otherwise.

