#### **10.2.1 PRIMARY ENDPOINT**

The primary endpoint is the level of stimulated c-peptide at 90-minutes derived from the mixed-meal tolerance test (MMTT) at 75±5 days following the first islet infusion. The difference in the means between the two treatment groups will be used as the measure of efficacy. Because the sample size is small, it is not practical to adjust for treatment center. The primary analysis will be based on an independent samples two-sided t-test. A difference will be declared statistically significant if  $p \le 0.05$ . The effect size will be estimated by the observed difference in the means for the two treatments. The estimated effect size and a 95% confidence interval for the effect size will be reported. If there is compelling evidence that the normal distribution does not hold then a logarithmic or square root transformation will be done before using the t-test. Appropriate adjustments will be made to compute the estimated effect size and its confidence interval.

The primary endpoint should be available in all randomized subjects. However, should a value not be available for a subject then a value will be imputed in one of two ways. If a value is observed for a subject after the 75 day period but before any subsequent islet infusion then that value will be used in the analysis. If no later value is available (e.g. the subject dies or withdraws from the study) then the lowest value observed for all subjects will be imputed for that subject. All imputations will be reported with the primary analysis. A secondary sensitivity analysis using multiple imputation methods will be performed to examine the effect of the choice of this imputation strategy.

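### Sections 10.2.1 and 10.6 give different final significance levels for the primary t-test, and the z cut-offs in 10.6 do not match its p-values for that test

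*Protocol*

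**What the plan says.** **Primary analysis (10.2.1).** "The primary analysis will be based on an independent samples two-sided t-test". The threshold follows: "A difference will be declared statistically significant if" p ≤ 0.05. The section does not mention interim looks or refer to 10.6.

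**Monitoring (10.6).** The plan uses the "Lan and Demets alpha spending method with an O'Brien-Fleming spending function". Its example has "planned interim analyses when 12 subjects (6 in each group) have finished the 75 day follow-up period", a second look at 24 subjects (12 per arm) and a final analysis at 36. On the underlying test it says: "These calculations were based on a 5% two-sided t-test to compare two independent means and no stopping for futility".

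The decision rules in the example are:

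- Look 1: stop "if the standard z-test for a difference in the two means exceeds 3.71 in absolute value", described as equivalent to p ≤ 0.0002.
- Look 2: stop if the test statistic exceeds 2.51 in absolute value, described as requiring p ≤ 0.0120.
- Final: superiority is concluded "if the difference is in favor of LMWDS and the p-value is less than or equal to 0.0463". The inferiority rule mirrors this, and a larger p counts as insufficient evidence of a difference.

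Table 7 (Stopping Boundary Values) lists ±3.71, ±2.51 and ±1.99 as Z-test boundaries, with associated p-values 0.0002, 0.0120 and 0.0463.

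**The concern.** There are two separate defects.

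1. **Two final thresholds.** If both example looks have been taken, a final p of 0.048 is a positive trial under 10.2.1 and a negative one under 10.6. Neither section says which prevails.

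2. **Two scales treated as one.** A cut-off of 3.71 and a p-value of 0.0002 are the same rule only when the statistic is normal. The planned test estimates its variance from 6, 12 or 18 subjects per arm, so the statistic has a t distribution on 10, 22 or 34 df. At look 1, any t statistic between 3.71 and 5.69 crosses the stated cut-off but misses the stated p-value. The monitoring board would then hold two conflicting instructions for the same data.

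What is at stake is the criterion for success on the primary endpoint and the rule for stopping early. Both should be unambiguous before any comparison by arm is made.

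**Working it through.** **Inputs, all from the protocol.** Two-sided 5% t-test (10.2.1, 10.4, 10.6); 18 per arm (10.4); looks at 6, 12 and 18 per arm (10.6), so df = 2n − 2 = 10, 22, 34 and information fractions are 1/3, 2/3, 1; z limits 3.71, 2.51, 1.99 and p-values 0.0002, 0.0120, 0.0463 (10.6, Table 7); SD 0.9 nmol/L and difference 1.0 nmol/L (10.4).

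**Step 1. Reproduce the stated boundaries.** O'Brien-Fleming-type spending with 2.5% per side is α(t) = 4·[1 − Φ(z₀.₉₈₇₅/√t)], with z₀.₉₈₇₅ = 2.241. Cumulative spend is 0.00021 at t = 1/3, 0.0121 at t = 2/3 and 0.05 at t = 1. Numerical integration of the known-variance process gives z = 3.710, 2.511, 1.993 and nominal p = 0.0002, 0.0120, 0.0463. The table is reproduced.

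**Step 2. Convert the z cut-offs to t-test p-values.** p = 2·P(T_df > c). The last column gives the t quantile that has the stated p-value.

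| Look | df | Cut-off | Stated p | p for a t statistic at the cut-off | t cut-off matching stated p |
|---|---|---|---|---|---|
| 1 | 10 | 3.71 | 0.0002 | 0.0040 | 5.69 |
| 2 | 22 | 2.51 | 0.0120 | 0.0199 | 2.74 |
| Final | 34 | 1.99 | 0.0463 | 0.0547 | 2.07 |

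**Step 3. Overall type I error under each reading.** Simulation of 4,000,000 null trials with cumulative pooled-variance t statistics at 6, 12 and 18 per arm; Monte Carlo standard error about 0.01 percentage points.

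| Rule applied | Type I error |
|---|---|
| Known-variance z against 3.71 / 2.51 / 1.99 | 5.0% |
| t-test p against 0.0002 / 0.0120 / 0.0463 | 5.1% |
| Same interim p-values, final p ≤ 0.05 | 5.4% |
| t statistic against 3.71 / 2.51, final p ≤ 0.0463 | 5.7% |
| t statistic against 3.71 / 2.51, final p ≤ 0.05 | 6.1% |
| t statistic against 3.71 / 2.51 / 1.99 | 6.5% |

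With no interim look, p ≤ 0.05 gives exactly 5%. On the known-variance scale, a single look at 12 subjects followed by 0.05 gives 5.01%; a single look at 24 (cut-off 2.51) followed by 0.05 gives 5.35%. The excess from 0.05 therefore comes almost entirely from the second look.

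**Step 4. Power.** A single t-test at 0.05 with 18 per arm, SD 0.9 and difference 1.0 nmol/L has 89.9% power. The sequential plan with the nominal p-values as limits has about 89.6%.

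**The case against.** The strongest defence is that 10.6 gives a p-value at every look and states the final decision in its text only as a p-value. Followed that way with the planned t-test, the error is 5.1%, essentially nominal. The 3.71 is attached by name to a z-test, for which the equivalence is correct, and the boundaries reproduce. The table is introduced as an example, interim analyses take place when requested (10.5), and monitoring details are left to the SAP. The 0.05 in 10.2.1 is right if no look is taken, and it equals the overall level of the spending plan.

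Most of this stands, and it rules out two stronger readings.

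- A reader might infer that the trial's real type I error is 5.4 to 6.5%. The documents do not support that: those figures apply only if 0.05 is used after the looks, or if t statistics are compared with the z column.
- A reader might infer that the board is told to stop at look 1 on evidence about 20 times weaker than stated (0.0040 / 0.0002 = 20). The text also gives the p-value limit, and a board supplied with t-test p-values would not stop at 0.0040.

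The defence does not remove the core. The protocol itself states both final levels and does not reconcile them. It also says the calculations rest on a t-test while presenting z cut-offs as equivalent to the p-values. Calling the schedule an example does not make that equivalence true on 10 df.

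**Conclusion.** The point holds as an inconsistency in the stated decision rules; the boundary calculation itself is correct. The unconditional 0.05 in 10.2.1 is wrong once alpha has been spent: about 5.4% if both example looks are taken with the p-value limits and 0.05 is used at the end. The z-to-p equivalence in 10.6 is false for the planned t-test at all three looks, most of all at the first. Across the rules a reader could take from the text, overall type I error runs from 5.1% (the p-values of 10.6 govern) to 6.5% (z cut-offs applied to t statistics throughout).

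These figures assume normal data with equal variances, looks at exactly 6, 12 and 18 per arm, and stopping whenever a limit is crossed. Other look times would change them. The SAP, which is not at hand, may settle which rule governs, but the protocol text would still need to agree with it.

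**What to change.** - **10.2.1:** replace the fixed p ≤ 0.05 with the nominal two-sided level left by the spending boundary of 10.6, that is 0.0463 if both example looks are taken and 0.05 only if none is. For any other schedule, the level follows from the spending function at the looks actually made.
- **10.6 and Table 7:** state that the decision limit at each look is the nominal two-sided t-test p-value (0.0002, 0.0120, 0.0463 in the example). Say that the z values are not to be compared with the t statistic, or replace them with the t quantiles 5.69, 2.74 and 2.07. Remove the statement that the z cut-off and the p-value are equivalent for this test.

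The cost is wording only. No change in sample size is needed: power for 1.0 nmol/L is about 89.6%, against 89.9% for a single test at 0.05.

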## 10.7 Reporting Deviations from Original Statistical Plan

The principal features of the study design and of the plan for statistical analysis of the data are outlined in this protocol and in the subsequent SAP. Any changes in these principal features will require a protocol or an SAP amendment, which would be subject to review by the independent DSMB, the study sponsor, and the health authorities. These changes will be described in the final report as appropriate.

## **11. IDENTIFICATION AND ACCESS TO SOURCE DATA**

# 11.1 Identifying Source Data

The investigator is required to keep accurate records to ensure that the conduct of the study is fully documented. The results of all clinical and clinical laboratory evaluations will be maintained in the subject's medical records and the data will be transferred to clinical CRFs.

Safety data will be recorded on CRFs specifically designed for this purpose. All data will be reviewed periodically by the DSMB and IRB. The DSMB and/or the IRB have the authority to withdraw any subjects and/or terminate the study because of safety findings.

## **11.2 Permitting Access to Source Data**

The investigational site participating in this study will maintain the highest degree of confidentiality permitted for the clinical and research information obtained from the subjects in this clinical trial. Medical and research records should be maintained at each site in the strictest confidence. However, as a part of the quality assurance and legal responsibilities of an investigation, the investigational site must permit authorized representatives of the sponsor(s), including pharmaceutical collaborators and their commercial partners, and health authorities to examine (and when required by applicable law, to copy) clinical records for the purpose of quality assurance reviews, audits, and evaluations of the study safety and progress. Unless required by the laws that permit copying of records, only the coded identity associated with documents or with other subject data may be copied (and all personally identifying information must be obscured). Authorized representatives as noted above are bound to maintain the strict confidentiality of medical and research information that is linked to identify individuals. The investigational site will normally be notified before auditing visits occur.

## **12.** QUALITY CONTROL AND QUALITY ASSURANCE

The investigator is required to keep accurate records to ensure that the conduct of the study is fully documented. The sponsor is responsible for regularly reviewing the conduct of the trial, for verifying adherence to the protocol, and for confirming the completeness, consistency, and accuracy of all documented data.

## 12.1 Compliance, Access, Entry and Handling of Study Data

The site Principal Investigator is required to keep accurate records to ensure that the conduct of the study is fully documented, and to ensure that CRFs are completed for all subjects according to study guidelines outlined in the study protocol and the Data System Users Instruction Manual.

Access to the data entry screens will be user ID and password protected. Each user will be provided with a unique personal ID and password. The investigational site participating in this study will maintain the highest degree of confidentiality permitted for the clinical and research information obtained from the subjects in this clinical trial. Medical and research records should be maintained at each site in the strictest confidence. However, as part of the quality assurance and legal responsibilities of an investigation, the investigational site must permit authorized representatives of the sponsor(s) and health authorities to examine (and when required by applicable law, to copy) clinical records for the purpose of quality assurance reviews, audits, and evaluations of the study safety and progress. Unless required by the laws that permit copying of records, only the coded identity associated with documents or with other subject data may be copied (and all personally identifying information must be obscured). Authorized representatives as noted above are bound to maintain the strict confidentiality of medical and research information that is linked to identified individuals. The investigational site will normally be notified before auditing visits occur.

During the course of the study, all data will be entered, stored, and managed in a relational database supported by database servers at the CIT-DCC. The results of all clinical and laboratory evaluations will be maintained in the subjects' medical records and the data will be transferred from these source documents directly to the electronic study Case Report Forms (CRF).

Once the analysis phase is complete, all clinical and mechanistic data will be archived for a minimum of 10 years. After 10 years, the data will be de-identified and archived for a minimum of 5 years. The data will be archived in the ImmPort System managed by the Northrop Grumman Information Technology Health Solutions team http://www.immport.org/immportWeb/home/home.do). The ImmPort System is a long-term, sustainable archive of data generated by investigators funded through the National Institutes of Allergy and Infectious Diseases (NIAID).

In order to maintain security, all data will be encrypted using the Secure Sockets Layer (SSL) protocol. This protocol allows an encrypted link to be established between the CIT-DCC web server and the computer at each center. In addition, the data will be verified by a series of computerized edit checks, and all relevant data queries will be resolved regularly. All discrepancies will be reviewed, and any resulting queries will be resolved with the site personnel and amended in the database.

All changes made to CRFs will be recorded in an electronic audit trail to allow all data changes in the data system to be monitored and maintained in accordance with federal regulations. Once a CRF is entered into the database and the person entering the data indicates that CRF is complete, any change to that data will be entered into the system's audit trail. The audit trail will record the CRF and variable that is changed, the old value, the new value, the date and time the change was made, reason change was made, and the user ID of the person making the change. Once a change is completed, the data system will re-validate all variables on that CRF. The changed CRF will be required to pass all validity and logic consistency checks. If any edit criteria fail, the system will generate appropriate queries. The clinical center coordinator will be asked to resolve the questions before the changes are completed.

The change system will allow certified CIT-DCC personnel and certified clinical center coordinators to make changes. Changes can be initiated by CIT-DCC monitors, CIT-DCC coordinators, and certified site personnel. Site personnel can access only the data for their own center. The system will generate weekly summary listings of all changes made to the database, the person making each change, and the reason for each change. These reports will be carefully reviewed by the CIT-DCC coordinator to monitor for unnecessary changes and/or problems with the data system.

# **13.** Ethical Considerations and Compliance with Good Clinical Practice

## 13.1 Statement of Compliance

This clinical study will be conducted using current good clinical practices (cGCP), as delineated in *Guidance for Industry: E6 Good Clinical Practice Consolidated Guidance*, and according to the criteria specified in this study protocol. Before study initiation, the protocol and the informed consent documents will be reviewed and approved by an appropriate EC or IRB, and the NIAID/NIDDK. Any amendments to the protocol or to the consent materials must also be approved by the IRB/IEC and submitted to the applicable Health Authorities before they are implemented.

## 13.2 Informed Consent and Assent

The informed consent form is a means of providing information about the trial to a prospective subject and allows for an informed decision about participation in the study. All subjects (or their legally acceptable representative) must read, sign, and date a consent form before entering the study, taking study drug, or undergoing any study-specific procedures. Consent documents not in the primary language of the subject must be translated into the subject's appropriate language. The informed consent form must be revised whenever important new safety information is available, whenever the protocol is amended, and/or whenever any new information becomes available that may affect participation in the trial.

A copy of the informed consent will be given to a prospective subject for review. The attending physician will review the consent and answer questions. The prospective subject will be told that being in the trial is voluntary and that he or she may withdraw from the study at any time, for any reason.

## 13.3 Declaration of Helsinki

This study will be conducted in accordance with the Declaration of Helsinki.

